Project title:

Use of Diced Cartilage for Management of Internal Mammary Vessel Exposure Sites in
Autologous Breast Reconstruction

Date: 10.07.2024

1) Studyprotocol

Procedures for informing and obtaining consent:

The recruited subjects will be informed about the nature, importance, risks (anonymizes data management) and scope of the intended scientific investigation in a personal conversation with one of the investigators and will receive patient information. After sufficient time for reflection, the consent will be confirmed in writing on the form prepared for this purpose - declaration of consent.

Measures:

This retrospective single-center cohort study included all autologous breast reconstructions performed from October 2021 to June 2023, in which diced cartilage (DC) was used to manage internal mammary vessel exposure sites (IMVES). These reconstructions will be divided into two groups: one with prior ipsilateral breast radiotherapy (DCR) and one without irradiation (DC) to evaluate the suitability of irradiated cartilage for the DC procedure. The control group consisted of an equal number of consecutive autologous breast reconstructions performed before the implementation of the DC procedure, for which rib cartilage segments were also removed but IMVES were managed conservatively. Controls will not be recruited during the period of DC use because initially, DC was not used consistently by all team members and may have been avoided in difficult reconstructions limiting the comparability of these patients. Data will be collected using electronic patient records, photographic documentation, and available postoperative MRI of reconstructed breasts.

Magnetic resonance imaging (MRI) scans performed at least 6 months postoperatively will be used to evaluate the sinking depth of epicostal soft tissue into the space of rib segment resection on axial planes (JiveX Software, VISUS Health IT GmbH, Bochum, Germany).

Postoperative photographic images will be examined by two investigators (blinded to group assignments) for IMVES-associated deformities using standardized photographic images of the reconstructed breasts at the 6-month follow-up.

2) Statistical Analysis Plan

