Statistical analysis will be performed using IBM SPSS Version 24 (IBM, Somers, NY, USA) and R 4.3.2 (R Core Team). Metrically scaled parameters will be assessed for a normal distribution using Shapiro–Wilk tests. Results for normal data will be presented as mean \pm standard deviation (SD) and will be analyzed using multi-factor variance analysis. Paired t-tests with Bonferroni correction will be used when significant differences were observed. Non-normally distributed metric parameters will be expressed as median (Q25–Q75) values and will be assessed using the Kruskal–Wallis test. Pairwise Mann–Whitney U tests with the Bonferroni correction will be used when significant differences were found. Categorical parameters will be assessed using the Chi-squared or Fisher tests, without tests for normality. Pairwise chi-square tests (or Fisher tests) with Bonferroni correction will be used when significant results were found. MRI data will be analyzed by isolating subgroups of the study population with MRI and applying pairwise case exclusions. A Chi-square test of independence will be performed to determine whether the groups differed significantly with regard to the presence of MRI. In addition, further comparison of the three groups will be carried out for the variables surveyed to clarify group differences. The significance level will be set at $\alpha = 0.05$ for all tests.

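### DC cases are chosen because DC was used, controls are consecutive earlier cases, and no case-mix adjustment is specified, so DC v control can be confounded; the roll-out part is probably small

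*Combined protocol and SAP*

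**What the plan says.** **Study protocol, Measures.** Cases are defined by treatment received: "This retrospective single-center cohort study included all autologous breast reconstructions performed from October 2021 to June 2023, in which diced cartilage (DC) was used". They are divided by prior ipsilateral radiotherapy into DCR (irradiated) and DC (not irradiated). For the comparator, "The control group consisted of an equal number of consecutive autologous breast reconstructions performed before the implementation of the DC procedure"; these had rib cartilage removed and conservative management. No split of the controls by radiotherapy is described. Concurrent controls are ruled out because "initially, DC was not used consistently by all team members and may have been avoided in difficult reconstructions limiting the comparability of these patients". On sources: "Data will be collected using electronic patient records, photographic documentation, and available postoperative MRI of reconstructed breasts".

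**SAP.** Normally distributed metric data "will be analyzed using multi-factor variance analysis", with no factors named. Non-normal metric data get Kruskal–Wallis and then Mann–Whitney tests. "Categorical parameters will be assessed using the Chi-squared or Fisher tests, without tests for normality". For sinking depth, "MRI data will be analyzed by isolating subgroups of the study population with MRI". A further three-group comparison of the recorded variables is planned. No matching, weighting, covariate list or exclusion of early cases is stated.

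**The concern.** The protocol names a selection process and applies it to one side of the comparison only. Taking earlier controls keeps the avoided difficult cases out of the control group, but does not put them back into the DC groups. A group selected on use of the procedure is then compared with an unselected consecutive series. If difficult cases were missed proportionately more often than easy ones, and if they have worse deformity or sinking depth (the documents state neither), part of a better DC result would be case mix.

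Radiotherapy is a second, separate source of imbalance. The DC group has none and the DCR group is all irradiated. If controls are mixed, each pairwise comparison with control differs in irradiation by construction. The planned comparison of recorded variables could reveal such a difference, but it would not remove it from the outcome result. DC v DCR is less directly exposed to the roll-out problem, because both groups are selected on DC use.

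**Working it through.** **No figure to reproduce.** The documents give no sample size, event rate, roll-out length or uptake. The only input taken from them is the window: October 2021 to June 2023 is 21 months. Everything else below is an assumption.

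**Assumptions.** DC has no effect. Deformity is a yes/no outcome with risk 20% in easy and 50% in difficult cases. The difficult share *q* is 0.2, 0.3 or 0.4, and cases accrue evenly. The roll-out covers the first *m* months of the window.

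**Formulas.**
- a = (m/21) × share of difficult roll-out cases missed; b = (m/21) × share of easy roll-out cases missed.
- Control risk = 0.5q + 0.2(1 − q).
- Difficult share among DC cases: q′ = q(1 − a) / [q(1 − a) + (1 − q)(1 − b)].
- DC risk = 0.5q′ + 0.2(1 − q′). Bias = control risk − DC risk; positive values favour DC.

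**Worked case.** m = 6, q = 0.3, half of difficult and 30% of easy roll-out cases missed. a = 0.143 and b = 0.086, so q′ = 0.3 × 0.857 / (0.3 × 0.857 + 0.7 × 0.914) = 0.287. Control risk is 29.0%, DC risk 28.6%, bias 0.40 points.

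| Roll-out | Easy missed | Difficult missed | Bias in points (q = 0.2, 0.3, 0.4) |
|---|---|---|---|
| 6 months | 30% | 50% | 0.30, 0.40, 0.46 |
| 6 months | 30% | 100% | 1.10, 1.47, 1.73 |
| 6 months | 0% | 50% | 0.71, 0.94, 1.09 |
| 6 months | 0% | 100% | 1.45, 1.97, 2.32 |
| 6 months | 30% | 30% | 0, 0, 0 |
| 6 months | 30% | 15% | −0.22, −0.29, −0.33 |
| 3 months | 30% | 50% | 0.14, 0.19, 0.22 |
| 3 months | 30% | 100% | 0.51, 0.68, 0.79 |
| 12 months | 30% | 50% | 0.68, 0.91, 1.05 |
| 12 months | 30% | 100% | 2.56, 3.56, 4.31 |

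For the first two rows the spurious odds ratio is about 0.98 and 0.92 to 0.94. With a weaker outcome link (20% v 30%), those rows fall to 0.10–0.15 and 0.37–0.58. The bias is zero if difficulty does not affect outcome, or if the roll-out ended before October 2021.

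**What the earlier controls achieve.** Concurrent controls would be the missed cases, with difficult share qa / [qa + (1 − q)b]. On the assumptions of the first two rows, the bias would be 3.13, 3.90, 4.25 and 8.73, 10.12, 10.42 points. The design choice therefore leaves about 10–11% (0.30/3.13 to 0.46/4.25) or 13–17% (1.10/8.73 to 1.73/10.42) of it.

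**What the model leaves out.** It covers roll-out selection only and says nothing about radiotherapy mix. The documents give nothing from which that could be sized.

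**The case against.** The strongest objection is that the bias is small next to the likely noise. Assume 50 to 200 reconstructions per arm and a 29% rate. The 95% half-width for DC v control is then 1.96 × √(2 × 0.29 × 0.71 / n), or about 18 to 9 points, against a bias of 0.3 to 1.7. Only a long roll-out with near-total avoidance gives more, which fits poorly with the protocol's own hedged wording. This stands, and it is why the roll-out part is rated small. It does not answer the radiotherapy imbalance, which arises from how the groups are defined.

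A second objection is that a multi-factor analysis implies factors beyond group. That is fair for normal metric data, where the criticism is only that the factors are unnamed. It does not reach categorical or non-normal outcomes.

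A third is that difficulty is not a defined variable, so adjustment may miss it. That also stands and limits what the fix can deliver.

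A reader might infer more than the documents support:
- **That the DC groups are known to lack difficult cases.** The protocol says only that avoidance may have occurred. That the window includes the roll-out is an inference.
- **That the bias must favour DC.** It is zero or reversed if difficult cases were missed no more often than easy ones.
- **That the deformity result is certain to be unadjusted.** The rating scale is not given; this holds only if the rating is categorical or non-normal.

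**Conclusion.** The concern holds in a limited form. Earlier controls remove most, not all, of the selection that the protocol names, and the plan specifies no adjustment for measured case mix where outcomes are categorical or non-normal. DC v control can therefore be confounded, including by prior radiotherapy.

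The roll-out part is of unknown and probably small size. A 6-month roll-out gives about 0.3 to 1.7 points with 30% of easy cases missed and up to 2.3 with none missed. This rests on assumed risks of 20% and 50%, a difficult share of 20–40% and even accrual. The radiotherapy part is not sized.

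This does not invalidate the study or the choice of earlier controls. Severity is minor to moderate.

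**What to change.** 1. **Adjusted comparison.** Keep the three-group analysis. Add one supportive comparison of DC and DCR together v control, adjusted for prior ipsilateral radiotherapy and a very short list of recorded pre-operative variables, fixed before outcomes are examined. Match the model to the outcome scale: logistic if deformity is binary, penalised if events are few; linear for sinking depth in the MRI subgroup. Use patient-clustered standard errors if any patient contributes two reconstructions.
2. **Reporting.** Give the implementation date and the number of rib-resection reconstructions without DC from October 2021 to June 2023. State residual selection as a limitation of the DC v control conclusion.
3. **Optional.** A sensitivity analysis could count DC cases only from a later start date fixed in advance, keeping all controls. It would not be decisive: a changed estimate could reflect selection, early experience or calendar time, and agreement would not exclude selection. Dropping 6 of 21 months with even accrual keeps k = 15/21 of DC cases. With equal arms and equal variance, the interval widens by √((1/k + 1)/2) = √1.2 = 1.10, about 10%.

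**Cost.** SAP wording, some extra record review, one date and one count. The downsides are overfitting if events or MRI scans are few, and only partial capture of difficulty by recorded variables. Adjustment for radiotherapy also works best if the controls include both irradiated and non-irradiated breasts, which the documents do not state.

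### MRI sinking depth has no upper time limit or scan-selection rule, and all controls predate all DC/DCR cases, yet no planned check or adjustment names the surgery-to-MRI interval

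*Combined protocol and SAP*

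**What the plan says.** All of the timing rules are in section 1) Studyprotocol, under Measures.

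- **MRI outcome.** "Magnetic resonance imaging (MRI) scans performed at least 6 months postoperatively will be used to evaluate the sinking depth of epicostal soft tissue" into the resected rib space. The source is "available postoperative MRI of reconstructed breasts", so there is no scheduled imaging visit. No latest scan time, data cut-off or rule for choosing among several scans is given.
- **Groups.** DC and DCR cases were operated on from October 2021 to June 2023. Controls are "consecutive autologous breast reconstructions performed before the implementation of the DC procedure", and none are taken from the period of DC use.
- **Photographic outcome.** This one has a fixed time point: "standardized photographic images of the reconstructed breasts at the 6-month follow-up".

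Section 2) Statistical Analysis Plan limits the MRI analysis to patients with a scan and adds one MRI-specific check: "A Chi-square test of independence will be performed to determine whether the groups differed significantly with regard to the presence of MRI". Normally distributed measures "will be analyzed using multi-factor variance analysis", with no factor or covariate listed. Non-normal measures "will be assessed using the Kruskal–Wallis test", followed by pairwise Mann–Whitney tests. The section also promises that "further comparison of the three groups will be carried out for the variables surveyed to clarify group differences", without listing the variables. The surgery-to-MRI interval is not mentioned in either section.

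**The concern.** Group and calendar period are completely separated: controls come first, and DC and DCR follow. If images are collected up to one common date, a control can have a scan at a longer interval after surgery than any DC or DCR case can. A minimum of 6 months equalises the start of the window but not its end.

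If sinking depth continues to change after 6 months, and if controls were in fact scanned later, the control contrasts in depth mix the effect of technique with the effect of time since surgery. The planned check on MRI presence would not show this. Two groups can have the same proportion scanned and very different scan times. The rank-test route takes no covariate, so if depth fails the normality test the main comparison cannot adjust for the interval at all.

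The missing selection rule leaves a related gap. Where a breast has several eligible scans, the plan leaves open which one supplies the depth value.

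**Working it through.** The documents give no scan dates, interval, rate of change in depth or number of MRIs, so there is no plan figure to reproduce. What can be worked out is how far the possible intervals differ, and how large a mean gap could follow under stated assumptions.

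**Step 1. Possible follow-up (months = days / 30.44).** The surgery dates come from Measures, taking the first and last day of the stated months. The cut-off is an assumption: the document date, 10.07.2024.

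- Last DC/DCR surgery, 30.06.2023: 376 / 30.44 = 12.35 months.
- First DC/DCR surgery, 01.10.2021: 1013 / 30.44 = 33.28 months.
- Controls: more than 33.28 months. If they span the L months just before October 2021 (assumed L = 6, 12 or 21), the upper end is about 39, 45 or 54 months.

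**Step 2. Form of the bias.** With the same linear drift in every group:

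bias in depth contrast = (mean control interval − mean DC/DCR interval) × change in depth per month.

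The documents give neither factor. If either is zero, the bias is zero.

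**Step 3. Range of the first factor.** Assume uniform accrual in each period and five possible scan-time patterns. F is a breast's possible follow-up at cut-off. Patterns (a) to (d) were run in two ways: each breast weighted equally with its scan time truncated at F, and scans counted only if they fall before F. The ranges span both versions and all three values of L. For pattern (e), the mean scan time is (6 + F)/2, so the gap is (20.93 + L)/4, where 20.93 = 33.28 − 12.35. The cut-off cancels.

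| Assumed scan timing | Gap at 10.07.2024 | Gap at 31.12.2024 | Gap at 10.07.2025 |
|---|---|---|---|
| (a) uniform, 6–12 months | 0 | 0 | 0 |
| (b) uniform, 6–18 months | 0.28–0.38 | 0 | 0 |
| (c) 6 months + exponential, mean 6 | 1.05–1.24 | about 0.6 | about 0.3 |
| (d) 6 months + exponential, mean 12 | 2.73–3.90 | 2.2–3.0 | 1.7–2.2 |
| (e) uniform from 6 months to cut-off | 6.7–10.5 | 6.7–10.5 | 6.7–10.5 |

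Pattern (e) for L = 6, 12 and 21 gives 26.93/4 = 6.7, 32.93/4 = 8.2 and 41.93/4 = 10.5 months.

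The gap is zero if scans cluster within 6 to 12 months. It is large only if scans extend far into follow-up, which the absent upper limit permits but nothing in the plan indicates. Later cut-offs shrink the gap under (b) to (d), because the DC/DCR cases then also have time to reach the later scan times. A cut-off before the document date would enlarge it, but none is shown, because the plan describes data collection in the future tense.

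**The case against.** The strongest reply is that the harm needs two facts the documents do not supply: that depth changes after 6 months, and that controls were actually scanned later. Only a longer possible interval is documented. That stands, and it limits the point to a risk.

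A reader might infer that the controls were scanned later, or that the MRI comparison is biased in a known direction. The documents support neither. They contain no scan dates and nothing on the course of sinking depth. Equally, they do not claim that depth is stable after 6 months, so the 6-month minimum does not settle the matter.

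A second reply is that the unlisted surveyed variables, or the unlisted factors of the variance analysis, may include the interval. They may, so it would go too far to say that the plan ignores timing. But nothing commits the analysts to look at it. A group comparison of intervals could reveal an imbalance without adjusting the depth contrast, and the multi-factor route is not used if depth is non-normal.

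Third, the scope is narrow. DC and DCR share one accrual period, so the calendar argument does not reach the comparison meant to judge irradiated cartilage. The photographic outcome is fixed at 6 months. Both limits stand.

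Finally, the added models could be made conditional on an observed imbalance. Reporting the interval is indeed the core request. Fixing the models in advance as sensitivity analyses avoids deciding on them after the depths are known.

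**Conclusion.** The point holds as a potential, undemonstrated confounder of two contrasts only: DC versus control and DCR versus control on MRI sinking depth. The plan's own rules create unequal possible intervals, and no planned check or adjustment names the interval.

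The size of any bias is unknown and may be zero. At a cut-off of 10.07.2024 the illustrative mean gap is 0 to 3.9 months, or up to 10.5 months under the most extreme pattern. All of these figures rest on the assumed cut-off, uniform accrual, controls placed directly before October 2021, and the assumed scan patterns. They are gaps in time, not effects on depth, and no effect size can be derived from them. This is a cheap improvement to the plan, not a reason to discount its MRI results in advance.

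**What to change.** In section 1), state the data cut-off and one scan rule, set without knowledge of the depth results and applied to every group. An example is the first eligible MRI at 6 months or later for each breast.

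In section 2):

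- Report the surgery-to-MRI interval by group (median, quartiles, range).
- Beside the planned comparison, add a sensitivity analysis of depth adjusted for the interval: analysis of covariance, or a rank-based or transformed version if depth is non-normal.
- Add a second sensitivity analysis restricted to an interval window that all groups can reach at the stated cut-off. For example, 6–12 months is reachable by every DC/DCR case at 10.07.2024, where the shortest possible follow-up is 12.4 months. With a cut-off before 30.06.2024 the latest cases would not reach 12 months, and the window would need to be shorter.

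The cost is a few lines of text. Surgery and scan dates should already be in the electronic records the study uses, and no new imaging is needed. The adjusted analysis spends one degree of freedom and assumes the same drift in all groups, so it does not remove the bias if drift differs by technique. The restricted analysis uses fewer scans.

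### Deformity is scored as it looks at 6 months and sinking depth on any later MRI, with no step to identify breasts already corrected at the vessel exposure site

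*Combined protocol and SAP*

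**What the plan says.** The protocol, under Measures, has two image-based outcomes.

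- **Photographs.** "Postoperative photographic images will be examined by two investigators (blinded to group assignments"), looking "for IMVES-associated deformities using standardized photographic images of the reconstructed breasts at the 6-month follow-up". This is a single reading at one time point.
- **MRI.** "Magnetic resonance imaging (MRI) scans performed at least 6 months postoperatively will be used to evaluate the sinking depth of epicostal soft tissue" at the resected rib segment. The window has a lower limit and no upper limit.

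On sources, "Data will be collected using electronic patient records, photographic documentation, and available postoperative MRI of reconstructed breasts". Corrective procedures are not named as an item to collect. On controls, "The control group consisted of an equal number of consecutive autologous breast reconstructions performed before the implementation of the DC procedure", so they come from an earlier calendar period than the diced cartilage cases.

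The Statistical Analysis Plan section adds two relevant rules: "Categorical parameters will be assessed using the Chi-squared or Fisher tests, without tests for normality", and "MRI data will be analyzed by isolating subgroups of the study population with MRI and applying pairwise case exclusions". It also tests whether the groups differ in having an MRI at all. Neither section mentions a second procedure at the exposure site, or gives a composite, exclusion or sensitivity rule for a breast that had one.

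**The concern.** A correction done because the site was deformed is a consequence of the outcome being counted. If it comes before the photograph and succeeds, the rating is a wrong value for how the first operation turned out. In a control, conservative management is credited with the result of a second procedure; in a diced cartilage case, the cartilage gets that credit. Blinding the raters to group does not help, because the photograph need not show that the site was operated on again.

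The comparisons at stake are diced cartilage against control and, if irradiated cartilage behaves differently, irradiated against non-irradiated diced cartilage. The MRI outcome is exposed in a different way. It is a depth and not a yes/no rating, so a post-correction scan could only give too small a depth, and only where the correction reached the tissue being measured.

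**Working it through.** **Is there a rule?** The photographic and MRI rules, the data sources and the SAP rules for categorical and MRI data were read together. The SAP deals with MRI availability and nothing else of this kind. No text records, excludes or reclassifies a corrected breast. The documents also state no sample size, power, deformity rate or correction rate, so there is no planned figure to reproduce.

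**Inputs, all assumed.** True deformity rates p_C = 30% in controls and p_D = 10% with diced cartilage; r_C and r_D are the shares of deformities corrected before the photograph so that none is visible. For power, 50 breasts per group and two-sided 0.05 without the Bonferroni step (the SAP gives alpha 0.05 without saying one- or two-sided).

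**Formulas.**
- Observed rate = p × (1 − r); hidden cases per 100 breasts = 100 × p × r.
- Observed difference = (p_C − p_D) − (p_C r_C − p_D r_D).
- Observed risk ratio = (p_D / p_C) × (1 − r_D) / (1 − r_C).
- Power = Φ[(d − 1.96 × SE0) / SE1], where d is the observed difference and SE0 and SE1 are its pooled and unpooled standard errors. At r = 0: d = 0.20, SE0 = √(0.2 × 0.8 × 2/50) = 0.080, SE1 = √((0.21 + 0.09)/50) = 0.0775, so Φ(0.56) = 71%.

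**Equal shares (r_C = r_D = r).**

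| r | Control | Diced cartilage | Difference (points) | Risk ratio | Hidden per 100 (control / DC) | Power |
|---|---|---|---|---|---|---|
| 0% | 30% | 10% | 20 | 0.33 | 0 / 0 | 71% |
| 5% | 28.5% | 9.5% | 19 | 0.33 | 1.5 / 0.5 | 68% |
| 10% | 27% | 9% | 18 | 0.33 | 3 / 1 | 65% |
| 20% | 24% | 8% | 16 | 0.33 | 6 / 2 | 59% |
| 50% | 15% | 5% | 10 | 0.33 | 15 / 5 | 38% |

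The absolute difference shrinks by the factor (1 − r), and power falls with it. The risk ratio does not move.

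**Unequal shares.**

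| r_C | r_D | Observed rates | Difference (points) | Risk ratio |
|---|---|---|---|---|
| 50% | 0% | 15% v 10% | 5 | 0.67 |
| 25% | 50% | 22.5% v 5% | 17.5 | 0.22 |
| 10% | 50% | 27% v 5% | 22 | 0.19 |

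The difference shrinks when p_C r_C exceeds p_D r_D, which at these rates means r_D below three times r_C. Otherwise it is unchanged or widens. The risk ratio moves towards 1 only if r_C exceeds r_D, so in the second row the difference shrinks while the risk ratio moves away from 1.

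**MRI window.** Diced cartilage cases run from October 2021 to June 2023. If the technique was introduced at about the start of that window (an inference), and the protocol date of 10.07.2024 is taken as the end of follow-up (an assumption), controls had at least about 33 months in which a scan could fall, against about 12 to 33 months for diced cartilage cases. That is calendar time available. Actual scan dates are not given.

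**The case against.** The strongest reply is that nothing in the documents shows that any breast was corrected before imaging. For the photograph, the correction would have to fall between reconstruction and the 6-month follow-up. If none did, no result changes. This stands, and it limits the point to a possible bias. Low shares also have to be shown: at 5% the difference loses one point in 20. A partial correction may still be rated as deformed, so only corrections that leave nothing visible count towards r.

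A reader might infer that failures are hidden mainly in controls, so that the plan is biased against diced cartilage. The documents do not support that. It needs correction shares that are similar between groups or higher in controls, and they give no shares; the 10% v 50% case favours diced cartilage. A reader might also infer that MRI would score a corrected breast as having no deformity. It would not: MRI measures depth at the rib defect, which a surface contour correction may leave unchanged.

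Two objections concern the remedy. Limiting the main depth analysis to pre-correction scans would drop corrected breasts whose only scan came afterwards, and these are selected failures. That is right, so the restriction belongs in a sensitivity analysis. Reclassifying on the recorded indication also sets aside a blinded rating in favour of a judgement by staff who knew the treatment, in records from two eras. That is a real cost. It is a reason to show both results side by side; it does not justify leaving a corrected deformity scored as absent.

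**Conclusion.** The gap is real and its effect is conditional. As written, a deformity successfully corrected before the 6-month photograph would be scored as absent, and a post-correction MRI would be used without a flag. Whether this happened, and in which group more often, cannot be told from the documents.

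Under the assumed 30% v 10% and equal shares, the loss runs from 1 point (5% corrected) to 10 points (50% corrected) out of 20, with the risk ratio unaffected. With unequal shares the error can go either way, so no direction should be claimed in advance. The point deserves a change to the plan because the rule is cheap to add, and because a count of zero corrections would itself settle the matter for the reader.

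**What to change.** 1. Extract from the electronic patient records the date and indication of every corrective procedure at the vessel exposure site, and report the counts by group, including zero. Whoever classifies the indication should be blinded to group where the record allows.
2. In the deformity endpoint, count a breast corrected for an IMVES deformity before the 6-month photograph as deformity present. Show the blinded as-photographed result beside it.
3. Keep all eligible MRIs in the main depth analysis and flag those taken after a correction. Add a sensitivity analysis limited to pre-correction MRIs, stating that it drops selected failures.

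The cost is one extra extraction item from a source the study already uses, and a few sentences in Measures and in the SAP. The downside is that the recorded indication is an unblinded clinical judgement, and recording and revision practice may differ between the historical control period and the diced cartilage period. The report should say so.

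### Only the multi-factor ANOVA can adjust for confounders; metric outcomes reach it only by passing Shapiro–Wilk, categorical outcomes never do, and its factors are not named

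*Combined protocol and SAP*

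**What the plan says.** Part 2 (Statistical Analysis Plan) sorts outcomes into three routes.

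- **Metric, judged normal.** The sorting step is "Metrically scaled parameters will be assessed for a normal distribution using Shapiro–Wilk tests". Outcomes that pass "will be analyzed using multi-factor variance analysis", followed by Bonferroni-corrected t-tests. The factors of the ANOVA are not listed.
- **Metric, judged non-normal.** "Non-normally distributed metric parameters will be expressed as median (Q25–Q75) values and will be assessed using the Kruskal–Wallis test". The follow-up is also covariate-free: "Pairwise Mann–Whitney U tests with the Bonferroni correction will be used when significant differences were found".
- **Categorical.** "Categorical parameters will be assessed using the Chi-squared or Fisher tests, without tests for normality".

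No regression, stratification, matching or weighting is named. The closing plan to compare the three groups further on the surveyed variables would describe imbalances but does not adjust for them.

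The design is in part 1, under Measures: "This retrospective single-center cohort study included all autologous breast reconstructions performed from October 2021 to June 2023". Controls are an equal number of consecutive reconstructions from before the new procedure was introduced. Two outcomes are described. MRI "will be used to evaluate the sinking depth of epicostal soft tissue into the space of rib segment resection on axial planes", which is metric. For the second, "Postoperative photographic images will be examined by two investigators (blinded to group assignments) for IMVES-associated deformities"; its scale is not stated, but presence or grade would be categorical.

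**The concern.** Nothing in this design balances the groups, so prognostic factors may differ between them. Radiotherapy is one documented candidate: it splits the diced-cartilage reconstructions into DCR and DC, while no such split is stated for the controls. The protocol itself shows awareness of case mix, since it rejects concurrent controls on the ground that diced cartilage may have been avoided in harder cases.

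Whether to adjust should follow from the design. For a metric outcome it follows instead from a normality p-value, which says nothing about confounding. The two metric routes also answer different questions: one can compare groups at fixed levels of another factor, the other cannot. A categorical outcome has no adjusted route at all. At stake is whether a significant group difference reflects the procedure or a recorded factor that happened to differ.

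**Working it through.** The documents give no sample size, SD, event rate or distribution, so there is no stated figure to reproduce. Every numerical input below is an assumption, and the results show direction and possible size only.

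**1. Can the same outcome land in either route?** Share of samples in which Shapiro–Wilk at 0.05 rejects (pooled values, 4,000 runs per cell):

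| Shape | N=20 | 30 | 60 | 90 | 150 |
|---|---|---|---|---|---|
| Normal | 5% | 5% | 5% | 5% | 5% |
| Gamma, shape 8 | 17% | 24% | 47% | 66% | 89% |
| Gamma, shape 4 | 29% | 44% | 78% | 94% | 99.7% |
| Lognormal, log SD 0.5 | 52% | 74% | 97% | 99.7% | 100% |

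For a fixed skewed shape, the route depends largely on how many MRIs happen to exist.

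**2. What does an omitted factor cost?** Assume two groups of n, no true group effect, and a binary factor x with prevalence 0.30 v 0.60. The outcome is y = e + b·x, where e has SD 1 and b is 0.5 or 0.8.

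Hand approximation for an unadjusted comparison of means:

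- Spurious difference = (0.60 − 0.30)·b = 0.3b.
- Standard error = √{[(1 + 0.21b²) + (1 + 0.24b²)]/n}, since 0.3 × 0.7 = 0.21 and 0.6 × 0.4 = 0.24.
- δ = difference / standard error. False-positive rate = Φ(δ − 1.96) + Φ(−δ − 1.96).

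Example, n = 60 and b = 0.5: difference 0.15; standard error √(2.1125/60) = 0.188; δ = 0.80; rate = 0.123 + 0.003 = 12.6%.

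Simulation with gamma (shape 2) errors, 4,000 runs per cell. The routed column uses Mann–Whitney if Shapiro–Wilk rejects and otherwise a linear model containing x:

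| Groups | b | Hand formula | Routed by Shapiro–Wilk | Mann–Whitney always | Linear model with x, HC3 |
|---|---|---|---|---|---|
| 24 v 24 | 0.5 | 8.0% | 8.7% | 9.2% | 4.3% |
| 24 v 24 | 0.8 | 12.2% | 11.8% | 13.8% | 4.5% |
| 60 v 60 | 0.5 | 12.6% | 15.8% | 15.8% | 4.8% |
| 60 v 60 | 0.8 | 23.3% | 30.3% | 30.4% | 4.9% |
| 60 v 60 | 0 | 5.0% | 5.3% | 5.3% | 4.9% |

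Repeat runs put the routed column at 7.6–8.7%, about 10–12%, 14.5–16.6% and 29–31% for the first four rows.

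**3. Is the excess due to the pre-test?** No. Omitting the pre-test and always using Mann–Whitney gives the same rates at 60 v 60 and slightly higher ones at 24 v 24. With b = 0 there is no excess. With milder skew (gamma shape 8, 60 v 60, b = 0.5) the routed rate is 10.2%, against 13.0% for Mann–Whitney always. It is lower only because the simulated ANOVA branch contains x, which the SAP does not promise.

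**4. Three groups, nearer to the plan's omnibus tests.** Lognormal depth (log SD 0.5), groups of 30/15/15 or 60/30/30, factor in 30% of controls v 50–60% of both diced-cartilage groups, effect 0.5–0.8 SD on log depth. For deformity, a 20% base rate and an odds ratio of about 2.3–3.9. 2,000 runs per cell:

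- Kruskal–Wallis: 6.9–17.0%.
- Chi-squared on deformity: 5.9–15.3%.
- Linear model on log depth with the factor: 4.2–5.7%.
- With no imbalance, all three: 4.2–5.9%.

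An adjusted model for deformity was not simulated.

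**The case against.** The strongest reply is that Shapiro–Wilk is not the culprit, and much of that stands. A reader might infer four stronger things that the documents do not support:

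- **That the normality test inflates the error rate.** Step 3 shows that it does not. The inflation belongs to the omitted factor.
- **That deformity is unadjusted because of the normality test.** The SAP exempts categorical outcomes from that test; their scale alone sends them to chi-squared or Fisher tests. Removing the test would change nothing for deformity.
- **That passing the test secures adjustment.** The ANOVA factors are unnamed and may include no confounder, and the follow-up t-tests carry none.
- **That sinking depth will fail the test.** The documents give no distribution or sample size, and do not say whether the test is applied pooled, by group or to residuals. At n = 48, a normal variable censored at zero with its mean 2 SD above zero is rejected in only 5% of samples. By group at n = 12, half-normal and gamma shapes are rejected in 11–29%.

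It is also fair that the two-group simulation is not the plan's procedure, which has three groups, an omnibus test and Bonferroni-corrected pairs. The three-group check covers the omnibus stage and points the same way.

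What survives is the structure. Only one route can adjust, a test unrelated to confounding guards it for metric outcomes, categorical outcomes have no such route, and no confounder is named.

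**Conclusion.** The point holds in this limited form: confounder adjustment is not assured for any outcome, and for a metric outcome its very possibility depends on a normality p-value. If a recorded prognostic factor is imbalanced, the unadjusted tests run above 5%: about 8–12% at 24 v 24 and 15–30% at 60 v 60 on the two-group assumptions, and 5.9–17.0% on the three-group ones. With the factor in the depth model the rate is 4–5% (two groups) or 4.2–5.7% (three groups).

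These figures rest on assumed prevalences, effects, group sizes and skew. They shrink with milder skew and vanish without imbalance. The 30% figure should not be read as the plan's error rate; it is one scenario with a strong factor and large groups. The plan should be changed because the better method is specific and cheap, not because a particular bias has been shown.

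**What to change.** 1. Stop using Shapiro–Wilk to choose the analysis. Check residuals as a diagnostic only.
2. Specify in advance one covariate-adjusted model per outcome, with a short named list of factors available in the patient records. For example, use a linear model with robust (HC3) standard errors for sinking depth, and logistic regression for deformity, Firth-penalised if events are sparse. Let the number of events limit the factors in the deformity model. Other adjusted methods would also serve; naming one in advance is what matters.
3. Handle radiotherapy explicitly. It defines DC v DCR and cannot be adjusted away in that contrast. In the comparison of diced cartilage with controls it should be a factor, with the controls' irradiation status taken from the records.
4. Keep Kruskal–Wallis and chi-squared or Fisher tests as unadjusted supportive results.
5. State that adjustment covers recorded factors only and does not remove calendar-period effects from historical controls.

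The cost is SAP wording, extraction of the named factors from records already in use, and a few lines of R, which the SAP already names. The downside is that with few deformity events the model can carry only a few factors.
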